1. PROTOCOL SUMMARY

Title: Topical Ruxolitinib (Jak1/Jak2 inhibitor) in Chronic Hand Dermatitis attenuates inflammation and enhances skin barrier repair.

Principal Investigator: [name] [name];
[contact]

Single site: Department of Dermatology - University of Rochester Medical Center, Rochester, NY

Study phase: Open label, proof of concept study

Population: Females and Male, age 18 - 75 years, who have moderate to severe Chronic Hand Dermatitis (CHD)

Number of participants: Up to 25 will be enrolled with 15 completing full study term

Intervention: Ruxolitinib cream 1.5% is an investigational drug that will be applied twice daily (BID) for 12 weeks (IND exempt) by the study participant. Ruxolitinib (Other Name: INCB018424) cream is a topical formulation applied as a thin film to affected areas.

Objectives and Endpoints:Primary objective & outcome:

1. To assess the efficacy of Ruxolitinib cream 1.5% on skin lesions in patients with Chronic Hand Dermatitis:

- proportion of patients achieving an Investigators Global Assessment (IGA) score of 0 or 1 with at least a 2-step improvement (IGA treatment success) at week 12
- Hand Eczema Severity Index (HECSI)-75% from baseline to week 12

Secondary objective & outcome:

- To assess the efficacy of Ruxolitinib cream 1.5% on other clinical domains:
Time to IGA treatment success
- Change in HECSI score from baseline to week 4, 8 and 12.
- Proportion of subjects with a ≥ 2 and ≥ 4 -point improvement in Itch Numerical Rating Scale (NRS) score from baseline to week 12.
- HECSI-75% at week 8
- HECSI-90% at week 12

2. To assess safety and tolerability of Ruxolitinib cream 1.5% in patients with chronic hand dermatitis:

- incidence, frequency and severity of adverse events and laboratory data for hematology, serum chemistry and urinalysis
- use of rescue medications

Exploratory objective & outcome:

1. To assess the effect of Ruxolitinib cream 1.5% on patient reported outcomes
 - Change from baseline to week 4, 8 and 12 in DLQI
 - Change from baseline to week 4, 8 and 12 in work productivity and activity impairment index
2. To assess the efficacy of Ruxolitinib cream 1.5% on skin barrier integrity in patients with Chronic Hand Dermatitis:
 - change in transepidermal water loss (TEWL) and barrier integrity score (TEWL recovery after tape stripping) and pH from baseline to week 4 and end of treatment on perilesion (normal appearing) skin
3. To identify translational skin biomarkers
 - change in the expression of selected biomarkers in skin samples obtained from tape stripping (d-squame) at baseline and end of treatment (week 12)
 - change in microbiome at baseline and end of treatment (week 12)

Treatment groups and Duration:

Will enroll up to 25 subjects with CHD; investigational drug will be applied twice a day for 12 weeks by the subjects. Subjects will be asked to come back for a safety follow up visit every 4 weeks until end of treatment.

2. STUDY RATIONAL

Background: Chronic hand dermatitis (also known as hand eczema; CHD) is one of the most disabling skin conditions that negatively affect quality of life and work capacity of affected patients. Hands and often wrists present with erythema, edema, scaling and fissuring accompanied by intense pruritus and pain. Thyssen JP et al, reported the point prevalence of hand dermatitis (1994-2007) was around 4%, the 1-year prevalence nearly 10%, whereas the lifetime prevalence reached 15%. A high incidence rate is associated with female gender, contact allergy, atopic dermatitis, and wet work environment.ⁱⁱ Hand dermatitis is a heterogeneous disease entity, with irritant and allergic contact dermatitis and atopic dermatitis (AD) as the main causative factors. The common denominator of CHD subtypes is a skin barrier dysfunction, which not only facilitates cutaneous penetration of allergens and irritants but also induces local immune activation. Currently, the management of CHD involves patient education about avoidance of irritants and allergens, skin protection measures, and topical (high and mid potency steroids, calcineurin inhibitors) or systemic anti-inflammatory therapy (e.g. corticosteroids,

[figure not shown]
alitretinoin, cyclosporine, methotrexate, azathioprine). Overall the rate of treatment success is poor with great dissatisfaction from patients and providers. While previous approaches to CHD have been focused on broad spectrum suppression of immune responses, we are interested in a targeted approach to restore proper skin barrier integrity and resistance to absorption of environmental allergens/hapten/irritant while also blocking the cytokine mediated inflammation.

It is our hypothesis that daily application of a topical JAK1/JAK2 inhibitor (Ruxolitinib) will induce clinical improvement of CHD by restoring skin barrier function and reducing skin driven inflammation.

Preliminary study: The epidermal skin barrier is composed of the stratum corneum (SC), which is made up of terminally differentiated keratinocytes surrounded by a complex lipid structure and the tight junctions (TJs), which are present just below the SC. TJs are made up of a number of adhesive and scaffolding proteins that control the passage of physiologic liquids, water, ions, and solutes through the paracellular pathway. Expression of key barrier proteins (e.g. claudin-1, loricrin, filaggrin and cytokeratin 10) was found to be reduced in biopsies from CHD patients. Notably, in patients treated with oral alitretinoin the improved expression of these markers correlated with clinical efficacy, suggesting that alitretinoin exhibits a disease-modifying activity by skin barrier repair mechanismⁱⁱⁱ.

Janus kinase (JAK) inhibitors block cytokine-mediated signaling via the Janus kinase-signal transducer and activator of transcription (JAK-STAT) pathway, which plays an important role in immunoregulation and cell growth. Furthermore, recent studies have shown a critical role played by JAK1 signaling in sensory neurons driven chronic itch^{iv}. JAK-STATs are heavily expressed in the epidermis and involved in critical epidermal barrier pathways. Studies on epithelial model have shown that JAKs play a role in TJ protein expression^v. Consistently, preliminary data generated in our laboratory showed that Ruxolitinib was able to rescue IFNy-induced TJ disruption (Fig 1).

Fig 1. In Primary human keratinocytes IFNy reduced TransEpithelial Electric resistance (TEER) and this was associated to disruption of TJ - Ruxolitinib (Rux) rescued IFNy induced TJ damage. A) TransEpithelial Electric resistance measures TJ integrity: reduced TEER reduced barrier integrity. B-D) Keratinocytes were stained with ZO-1 (TJ markers) 120hr post differentiation.

Design & Methodology. This is an investigator-initiated, proof of concept, open study to assess efficacy of a topical Ruxolitinib in subjects with CHD. The study will be conducted at the University of Rochester Medical center, Dermatology Department – Rochester, NY.

Qualified and enrolled subjects (see Inclusion/exclusion criteria) will be required to come to URMC Dermatology Clinic for at least five visits: visit 1 (V1, day 0), start of active treatment; visit 2 - 4 weeks treatment; visit 3 – 8 weeks and visit 4 – 12 weeks and end of the active study; visit 5 post treatment follow up, 4 weeks (V5, 112+/- 3 days post V1). To ensure feasibility of enrollment, and in subjects requiring a washout period, we will include a screening visit (up to 28 days +/- 3 prior to V1). As part of the screening, subjects with possible contact allergy dermatitis (CAD) will undergo PATCH testing (70 common allergens, North America series; see *exclusion criteria*) or they must have documentation of test performed 3 years prior screening. In patient with CHD avoidance of the allergens should be the first measure to ensure successful treatment. Subjects with known antigen sensitization based on Patch test (with 3 years) that are unable to reduce contact with the specific antigen(s) will be excluded.

We will also exclude patients with active lesions of Atopic Dermatitis and Psoriasis (see *exclusion criteria*), as they might need additional systemic or topical treatment that could indirectly affect hand dermatitis severity during the study.

Subjects will apply topical Ruxolitinib 1.5% cream twice a day for 12 weeks on eczematous areas of hands and adjoining clinically normal (perilesional) area. We included non-lesional/perilesional skin to evaluate the safety (e.g. irritant or toxic effects) of the compound on irritated/atopic skin, as those subjects have a lower irritancy threshold^{vi}. Also, skin barrier impairment (e.g. increase water loss/TEWL) can be already detected in normal appearing skin in atopic subjects and it is thought to allow penetration of haptens/allergens/irritants with consequent activation of an inflammatory response. It is our hypothesis that treatment with topical Ruxolitinib, a JAK1/JAK2 inhibitor, will normalize skin barrier integrity in perilesion skin. During the study, subjects will be allowed to stay on bland moisturizer and anti-histamine on a stabilized dose and expected to maintain this dose throughout the study. **In addition to clinical and safety outcomes**, the study design will include **exploratory** mechanistic outcomes, in a stepwise tactic. During the trial we will collect: 1) non-invasive skin barrier assessment (i.e. TEWL, SC integrity score); 2) stratum corneum extract to investigate potential biomarkers and skin microbiome (stored for future investigation); 3) Patient oriented outcomes. If the data gathered from the clinical trial demonstrates the clinical improvement we expect, the mechanistic studies will be extremely relevant to start clarifying specific target downstream to Ruxolitinib efficacy in CHD as well as biomarkers that could eventually be investigated in consequent larger clinical trials.

ADMINISTRATIVE ORGANIZATION

UR Dermatology at College Town is the only participating site in this research study.

3. STUDY POPULATION

Number of patients: Up to 25 total subjects. We might need to enroll additional subjects in case of subject early discontinuation to reach the total number of 15 evaluable subjects (complete data set).

Study population: Females and Male, age 18-75 years, who have Chronic Hand Dermatitis

Racial and Ethnic Origin: We will not have any restrictions based on racial or ethnic origin. We based our target research population racial and ethnic distribution on the data of the 2000 United States Census for the Monroe County Area.

Vulnerable subjects: We will not be targeting vulnerable subjects

Inclusion Criteria:

- Age 18-75 years.
- Diagnosis of chronic hand eczema defined as hand eczema, which has persisted for more than 3 months or returned twice or more within the last 12 months.
- Disease severity graded as moderate to severe according to IGA (i.e., IGA ≥ 2).
- Recent history (within 1 year before the screening visit) of inadequate response to topical corticosteroid and/or calcineurin inhibitors treatment or topical corticosteroid treatment being medically inadvisable.

Exclusion Criteria:

- Active atopic dermatitis in regions other than the hands requiring medical treatment.
- Active psoriasis in regions other than the hands requiring medical treatment.
- Clinically significant infection (e.g., impetiginized hand eczema or tinea manuum) on the hands.
- Patients with excessive contact of hands with water (longer than 2 hours a day; or > 20 hands washing at day) that is believed to be a predominant cause of the hand dermatitis.
- Subjects with known antigen sensitization based on Patch test (with 3 years) that are unable to reduce contact with the specific antigen(s).
- Subjects chronically and consistently exposed to known irritant or other substance known to impact skin barrier will be excluded based on PI judgement.
- Systemic treatment with immunosuppressive drugs, immunomodulating drugs, retinoids, or corticosteroids within 4 weeks prior to baseline.
- Systemic treatment with antibiotics within 4 weeks prior to baseline
- Phototherapy on the hands within 4 weeks prior to baseline.
- Use of topical immunomodulators (e.g., phosphodiesterase-4 (PDE-4) inhibitors, pimecrolimus, tacrolimus) or topical corticosteroids on the hands within 2 weeks prior to baseline.
- Use of topical antibiotics on the hands within 2 weeks prior to baseline.
- Change in systemic antihistamine therapy within 2 weeks prior to baseline i.e., subjects must not start antihistamine treatment or change the current dosage regimen within 2 weeks prior to baseline.

- Other topicals applied therapy on the hands (except for the use of subject's own emollients) within 1 week prior to baseline.
- Receipt of any marketed or investigational biologic agents within 6 months or 5 half-lives prior to baseline will be in the judgement of the investigator whether or not study drug may affect or interact with study drug's mechanism of action.
- Any disorder which is not stable and in the investigator's opinion could affect the safety of the subject, influence the findings of the trial, or impede the subject's ability to complete the trial.
- Participants with clinically significant cytopenia at screening.
- Participants with severely impaired liver or kidney function and unstable.
- Participants who have previously received JAK inhibitor therapy, systemic or topical.
- History of any known primary immunodeficiency disorder including a positive human immunodeficiency virus (HIV), or the subject taking antiretroviral medications.
- Females who are breastfeeding, pregnant, or anticipate becoming pregnant during the study time frame.
- History of skin cancer on hands within 5 years.
- History of recalcitrant warts on hands within 1 year.

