4. STUDY TREATMENT & DESIGN

Study design: This is an open label, proof of concept single site study and will be conducted at the Department of Dermatology, URMC

- Screening visit (-28 days before start of treatment)
- visit 1 - (V1, day 0), start of active treatment;
- visit 2 – 28 +/- 3 days (4 weeks) treatment;
- visit 3 – 56 +/- 3 days (8 weeks) treatment;
- visit 4 – 84 +/- 3 days (12 weeks) end of treatment
- visit 5 – 112 +/- 3 days (16 weeks) safety follow up 4 weeks post treatment
- during each visit a skin swab will be collected and stored in the lab for future microbiology study
- Skin Symptom questionnaire will be done during each visit.

Screening visit (-28 days)

- 1) Consenting and confirmation of inclusion & exclusion criteria
- 2) Medical history
- 3) Physical exam with focus on skin exam
- 4) Collection of concomitant medications
- 5) Fasting blood draw for safety labs (CBC with diff, Chemistry, Lipid panel)
- 6) Urinalysis
- 7) Possible washout period

- 8) Possible schedule PATCH test if investigator believes clinically necessary to r/o contact dermatitis
- 9) Urine Pregnancy test for woman of childbearing potential
- 10) Scheduling visit 1

Visit 1 (Day 0):

- 1) Confirmation of inclusion & exclusion criteria
- 2) General history
- 3) Physical exam
- 4) Review of concomitant medications
- 5) Urine pregnancy test for woman of childbearing potential at each visit. Counseling on acceptable birth control measures to use throughout treatment period including 30 days after stopping study drug (16 weeks or 112 days)
- 6) Clinical scores for chronic hand dermatitis
- 7) Itch and other QoL assessments; review daily diary
- 8) Digital pictures of the target area/hands
- 9) Non-invasive skin barrier Measurements: TransEpidermal Water Loss (TEWL) and optional pH may also be performed
- 10) Repeated tape stripping (Cuderm™ tape) of peri-lesional (0, 5, 10, 15, 20 tape) locations from treated area will be collected as part of the TEWL assessment and to assess for SC cohesion/integrity (rate of change in TEWL with repeated stripping). Serial measurements of TEWL will be performed after tape stripping as previously described^{vii}. This will also allow collecting proteins (eluted from the tape) for validation of biomarkers
- 11) Dispense Investigational drug for 4 weeks
- 12) Provide instructions to complete at home diary.
- 13) Provide date of Visit 2
- 14) Weight of the tube to check for subject's compliance
- 15) Skin swabs (optional)

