- **Disease status assessment:** **1)** Investigator Global Assessment (IGA), which will provide information of the overall disease (5-point scale: clear, almost clear, mild, moderate, severe) and it is the score requested by FDA for clinical study. Data will be reported as and **2)** Hand Eczema Severity Index (HECSI)^{viii}, a well-accepted and validated scoring system for disease activity. It incorporates both the extent and the intensity of the disease. Each hand is divided into five areas: fingertips, fingers (except the tips), palms, back of hands and wrists. Each area will be score for

extension and intensity of the six following clinical signs: erythema, induration/papulation, vesicles, fissuring, scaling and edema; which are graded on the following scale: 0, no skin changes; 1, mild disease; 2, moderate and 3, severe (see appendix). Data will be reported as percent change in HECSI score from baseline to week 4, 8 and 12.

The presence or absence of skin irritation (e.g. macular/papular eruption), redness, atrophy and telangiectasia will be noted at each study visit.

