6. DATA ANALYSIS AND DATA MONITORING

Objectives and Endpoints:

Primary objective & outcome:

1. To assess the efficacy of Ruxolitinib cream 1.5% on skin lesions in patients with Chronic Hand Dermatitis:

- proportion of patients achieving an Investigators Global Assessment (IGA) score of 0 or 1 with at least a 2-step improvement (IGA treatment success) at week 12
- HECSI-75% from baseline to week 12

Secondary objective & outcome:

1. To assess the efficacy of Ruxolitinib cream 1.5% on other clinical domains (e.g. pruritus, pain, work productivity and activity impairment; daily quality of life index/DLQI, Hand Eczema Severity Index/HESI):

- Time to IGA treatment success
- Change in HECSI score from baseline to week 4, 8 and 12.
- Proportion of subjects with a ≥ 2 and ≥ 4 -point improvement in Itch Numerical Rating Scale (NRS) score from baseline to week 4, 8 and 12.
- HECSI-75% at week 8
- HECSI-90% at week 12

2. To assess safety and tolerability of Ruxolitinib cream 1.5% in patients with chronic hand dermatitis:

- Incidence, frequency and severity of adverse events and laboratory data for hematology, serum chemistry and urinalysis
- use of rescue medications

Exploratory objective & outcome:

1. To assess the effect of Ruxolitinib cream 1.5% on patient reported outcomes

- Change from baseline to week 4, 8 and 12 in DLQI

- Change from baseline to week 4, 8 and 12 in work productivity and activity impairment index
2. To assess the efficacy of Ruxolitinib cream 1.5% on skin barrier integrity in patients with Chronic Hand Dermatitis:
- change in transepidermal water loss (TEWL) and barrier integrity score (TEWL recovery after tape stripping) and pH from baseline to week 4 and end of treatment on perilesion (normal appearing) skin
3. To identify translational skin biomarkers
- change in the expression of selected biomarkers in skin samples obtained from tape stripping (d-squame) at baseline and end of treatment (week 12)
4. To identify change in microbiome after treatment

Side effects and baseline characteristics will be tabulated qualitatively. The blinded pre- vs post evaluation will be analyzed for IGA scores by the Wilcoxon sign-rank test.

Data Storage and Confidentiality

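### The severity inclusion criterion says moderate to severe but sets the cut-off at IGA 2, which is mild on the protocol's own scale; any IGA-2 entrant would also face a stricter target for IGA treatment success

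*Combined protocol and SAP*

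**What the plan says.** Section 3 (Inclusion Criteria) sets the severity requirement as "Disease severity graded as moderate to severe according to IGA (i.e., IGA ≥ 2". The Population line of section 1 describes patients "who have moderate to severe Chronic Hand Dermatitis (CHD". The corresponding line in section 3 gives no severity: "Study population: Females and Male, age 18-75 years, who have Chronic Hand Dermatitis".

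Section 4 (Disease status assessment) describes the IGA as a "5-point scale: clear, almost clear, mild, moderate, severe" and prints no numbers beside the labels.

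Sections 1 and 6 list two primary outcomes. One is the proportion of patients with an IGA "score of 0 or 1 with at least a 2-step improvement (IGA treatment success) at week 12". The other is "HECSI-75% from baseline to week 12". Section 6 also lists "Time to IGA treatment success" as a secondary outcome. The only named IGA test is a Wilcoxon signed-rank test on scores before and after treatment. No analysis by baseline IGA is planned. The sample is up to 25 enrolled, with 15 completing.

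**The concern.** One sentence gives two eligibility rules that disagree about patients with mild disease. Screening staff could admit or refuse the same IGA-2 patient and cite the same criterion either way. The documents therefore do not fix who may enrol.

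The disagreement also reaches the endpoint. The requirement of at least a two-step improvement makes a difference only for patients entering at IGA 2, the group whose eligibility is in doubt. If they enrol, a week-12 score of 1 is a failure for them and a success for everyone else. The overall success proportion, and the time to success, then depend on how many mild patients happened to be recruited. There is no control arm in which the same case mix would appear. A report describing the results as applying to moderate-to-severe disease would be inaccurate.

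**Working it through.** **Step 1: number the scale.** Section 4 gives five ordered labels, and the primary outcome uses a score of 0. Five levels starting at 0 give clear = 0, almost clear = 1, mild = 2, moderate = 3, severe = 4. This is an inference, because the labels carry no printed numbers. The alternative coding of 1 to 5 does not help: 2 would then be almost clear, still below moderate, and the endpoint's score of 0 would not exist.

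**Step 2: look for another severity floor.** The remaining criteria in section 3 concern duration or recurrence, treatment history, exposures, washout and comorbidity. None sets a minimum current severity, such as a HECSI threshold.

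**Step 3: apply the success rule.** Success requires a week-12 score of at most 1, and baseline minus week-12 of at least 2.

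| Baseline IGA | Week-12 scores that count as success |
|---|---|
| 2 (mild) | 0 |
| 3 (moderate) | 0, 1 |
| 4 (severe) | 0, 1 |

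From 2 to 1 is one step and fails. Any move from 3 or 4 to 0 or 1 is already at least two steps.

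**Step 4: effect on the pooled proportion.** The documents give neither expected success rates nor expected numbers of mild patients, so both are assumed here. With m mild patients among 15 completers, success rate p at baseline 2 and 50% at baseline 3 or 4:

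pooled rate = (m × p + (15 − m) × 0.5) / 15

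| m | p = 20% | p = 50% | p = 80% |
|---|---|---|---|
| 3 | (0.6 + 6.0)/15 = 44% | 50% | (2.4 + 6.0)/15 = 56% |
| 5 | (1.0 + 5.0)/15 = 40% | 50% | (4.0 + 5.0)/15 = 60% |

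One patient in 15 is 1/15 = 6.7 percentage points. The sign of the shift is unknown: mild patients must reach a stricter end state but start nearer to it.

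**Step 5: effect on precision.** If 0, 3 or 5 of the 15 completers entered at IGA 2, the moderate-to-severe estimate rests on 15, 12 or 10 patients. Exact (Clopper-Pearson) 95% intervals near 50% are:

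| Successes / n | 95% interval | Width (points) |
|---|---|---|
| 8/15 | 26.6% to 78.7% | 52.1 |
| 6/12 | 21.1% to 78.9% | 57.8 |
| 5/10 | 18.7% to 81.3% | 62.6 |

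**Step 6: outcomes not affected by the two targets.** HECSI-75 asks the same relative improvement of every patient. The Wilcoxon test uses the paired scores and not the success rule.

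**The case against.** The strongest reply is that this is a small slip in an open-label, single-arm, proof-of-concept study. Section 1 and the words of the criterion both say moderate to severe, and only one number in brackets disagrees. There is a single site, so sites cannot differ in how they read it. Patients must also have had an inadequate response to topical treatment, or be unsuitable for topical corticosteroids. The success rule is clearly stated and the same for all; requiring two steps from a mild patient can be seen as conservative. Any harm needs mild patients to enrol and to respond at a different rate. The shifts in Step 4 rest on assumed rates and fall inside the 26.6% to 78.7% interval for 8/15, and the plan states no success threshold that they could cross.

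Much of this stands. The numerical effect is modest, its direction cannot be determined, and the two-step rule is not in itself an error. The contradiction remains. The treatment-history criterion looks back over a year and does not exclude a patient who is currently mild. Having one site does not tell its staff which half of the sentence to apply. The protocol refers to an appendix for scoring, which was not available for this review. If it numbers the IGA levels 0 to 4, that would confirm the conflict, not remove it.

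**Conclusion.** The criterion is wrong as written: its words and its number cannot both hold on the protocol's scale. This rests only on the five labels and the use of a score of 0 in the primary outcome, and not on any assumed rate. The documents do not show which version was meant.

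That an IGA-2 entrant would need to become clear, while others need only be almost clear, follows directly from the success rule. It affects one of the two listed primary outcomes and one secondary outcome, and only if such patients enrol. Under the assumptions shown, the pooled success rate could move by up to 6 points in either direction with three mild patients, or 10 points with five. No stated decision changes. Independently of direction, the interval for the moderate-to-severe group widens from about 52 points to about 58 or 63, unless further patients are enrolled within the cap of 25. The correction matters mainly because it decides who is enrolled and whom the result describes.

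**What to change.** Reconcile sections 1, 3 and 4 so that words and number agree, and print 0 to 4 beside the five IGA labels. There are two consistent versions, and the investigator needs to state which is intended:

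- **If moderate to severe is intended,** change the cut-off in section 3 to IGA ≥ 3. All entrants then share the same success target. The cost is a smaller eligible pool and possibly slower recruitment at the single site.
- **If IGA ≥ 2 is intended,** describe the population as mild to severe in sections 1 and 3. The cost is a broader conclusion and fewer than 15 moderate-to-severe completers, unless more patients are enrolled within the cap of 25.

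If any IGA-2 patients are enrolled, including any already enrolled under the present text, report IGA treatment success and time to IGA treatment success separately for baseline IGA 2 and baseline IGA 3 or more. A descriptive split is enough, with counts and, for the success proportion, exact confidence intervals. It uses the baseline score already collected at Visit 1 (item 6, "Clinical scores for chronic hand dermatitis"), so no new data are needed.

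The work is a short amendment touching a few lines, with the IRB approval that section 6 requires before implementation, and a small addition to the results tables.
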